Bupivacaine liposomal injectable suspension has been shown to improve analgesia scores and decrease opioid use when infiltrated locally at the surgical site in a variety of procedure types, including hemorrhoidectomy and bunionectomy.¹⁵⁻¹⁷ Similar results of lower pain scores and decreased opioid use with liposomal bupivacaine compared to standards of care have been shown for patients undergoing mammoplasty, ileostomy reversal, and open colectomy.¹⁸⁻²¹ Conventional bupivacaine, when administered as a single nerve block, has a duration of activity of 8 to 24 hours.²² Liposomal bupivacaine, given its prolonged release, has the potential to provide anesthetic activity at the nerve site beyond 24 hours. Animal studies and phase 1 trials in healthy volunteers have shown safety with use of liposomal bupivacaine as a peripheral nerve block.²³

Further investigation is needed to fully evaluate this route of administration. This study aims to assess the efficacy of liposomal bupivacaine when used as a regional block compared to standard of care for analgesia in trauma patients with rib fractures. This has only been done in case reports and preliminary studies to date.²⁴⁻²⁶

Study Justification

The potential utility of liposomal bupivacaine in trauma patients suffering from multiple rib or sternal fractures is unknown. Recent evidence has shown pharmacodynamic benefits of liposomal bupivacaine through prolonged pain relief and subsequent opioid reduction. The sustained analgesia may also reduce the likelihood of respiratory failure, development of pneumonia, increased length of stay, and patient mortality. The purpose of this study is to evaluate the efficacy of liposomal bupivacaine to provide analgesia via posterior intercostal nerve block following significant blunt chest trauma, minimizing adverse outcomes and length of stay and overall narcotic usage.

Intercostal nerve blockade has been chosen over paravertebral block, as the intent of the study is to identify a therapeutic strategy that can be employed based on standard training for emergency medicine or surgery practitioners. Both

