emergency medicine and surgery practitioners are familiar with intercostal blocks for placement of tube thoracostomy. Intercostal blocks do not require additional training, as would be done in the setting of a pain medicine fellowship, and do not incur the risks of hypotension associated with epidural catheters. Additionally, intercostal and paravertebral blocks carry similar risks of pneumothorax or intercostal neurovascular bundle injury.

Study design:

This is an investigator-initiated, single-center, prospective, double-blinded, placebo-controlled trial funded by the United States Air Force. Multi-system, adult trauma patients greater than or equal to 18 years of age admitted to the University of Cincinnati Medical Center (UCMC), an urban American College of Surgeons-verified Level 1 trauma center with more than 3500 annual trauma admissions annually will be identified by the research team. Patients will be screened and those who meet all inclusion/exclusion criteria will be approached for informed consent by study personnel in their rooms. Informed consent will be obtained prior to enrollment and any study procedures are done. Patients will then receive either receive 1 mL of liposomal bupivacaine just below each affected rib or 0.9% sodium chloride peri-intercostal subcutaneous injection (as placebo control) via a 25-G needle. Goal enrollment is 200 patients with 100 patients in each group. Patients included in the study will be followed during inpatient hospitalization through discharge.

6. Research data collection/study procedures:

Intervention

Patients will be identified on admission and will be screened by inclusion/exclusion criteria. After informed consent is obtained they will be randomized into one of two possible groups:

- a. Liposomal bupivacaine intercostal (group 1; interventional)
- b. 0.9% sodium chloride peri-intercostal subcutaneous (group 2; placebo-control)

Patients will be placed on continuous monitoring of heart rate, EKG, and pulse oximetry. Blood pressure and respiratory rate will be measured every 5 to 10 minutes during the procedure and every at least 15 minutes for the first hour after the procedure. All patients undergoing injection will remain on heart rate, EKG, and pulse oximetry monitoring by telemetry for 96 hours following injection.

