A chest xray will be obtained as clinically indicated following the procedure if there is concern for the development of pneumothorax.

Self-reported pain will be measured using the verbal NRS, a 0-10 ordinal scale (e.g., 0 = "no pain"; 10 = "worst pain imaginable").²⁷ Breakthrough opioid dosing

will be guided by a formal inpatient analgesia protocol. Pain assessments will occur every 6 hours or per standard of care for the appropriate setting (e.g., intensive care unit, trauma ward) for the first 96 hours. All opioid dosing will be converted to oral morphine equivalents for comparison purposes. Time to first breakthrough opioid dose will be recorded. Incentive spirometry will be used and assessed and recorded by respiratory therapist, with adjunct inspiratory assistance (e.g., EzPAP) applied per our institutional volume expansion protocol.

Follow-up will occur daily by study coordinators and trauma service physicians for the first 96 hours after block procedure, then daily by the trauma service physicians for 14 days or until discharge from the hospital if it occurs earlier.

Standard of care analgesia regimen on the trauma service will be provided to all patients enrolled in the study, regardless of liposomal bupivacaine or placebo injection. This regimen will be per the Trauma acute multimodality pain management protocol (Appendix).

Typical escalation of analgesics provided for these patients, as deemed medically appropriate based on age and comorbid medical conditions, includes (in order of addition to regimen):

- Acetaminophen, oral or enteral
- NSAIDs, ibuprofen or ketorolac
- Lidocaine 5% transdermal patch
- Oral or enteral tramadol
- Oral or enteral hydrocodone or oxycodone
- IV morphine or hydromorphone, intermittent dosing
- Patient controlled analgesia morphine or hydromorphone
- Long-acting narcotics, including methadone, oxycodone ER, or morphine ER
- Neuromodulating adjuncts, including gabapentin or pregabalin
- Epidural analgesia catheter placement

During this time all adverse events will be recorded. Subjects who experience serious adverse events will be followed until the event resolves. If necessary these patients will be followed up by weekly phone calls as well as at the standard of care clinic visit two weeks post-discharge.

Randomization

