Myalgia	No interference with activity	Some interference with activity	Significant; prevents daily activity	ER visit or hospitalization

Table 9.4 extracted from: Guidance for Industry, Toxicity Grading Scale for Healthy Adult and Adolescent Volunteers Enrolled in Preventive Vaccine Trials, U.S. Department of Health and Human Services, Food and Drug Administration, Center for Biologics Evaluation and Research, August 2016

Treatment of cardiovascular and neurologic adverse events

- Local anesthetic systemic toxicity
 - Treatment will be initiated as recommended as the American Society of Regional Anesthesia and Pain Medicine, according to the society's checklist (Appendix)
- Treatment will include: transfer to intensive care unit setting if not already in intensive care unit, continuous hemodynamic monitoring for at least 24 hours, appropriate airway management with assistance from respiratory therapy and a critical care consultant as needed, cardiovascular stabilization and assistance from a critical care consultant as needed, administration of Lipid Emulsion therapy, as per ASRA checklist in Appendix, Neurology consult for any observed systemic neurologic toxicity (including change in vision, mental status change, persistent headache, seizure), Cardiology consult for any arrhythmias that persist greater than 30 minutes, beyond initial appropriate medical treatment, or result in hypotension with systolic blood pressure < 80mmHg.

10. Data Safety monitoring plan and/or DSMB:

Patients will be screened for the adverse events described above.

Adverse events will be continuously assessed on an ongoing basis by [name], medical monitor. Study will be stopped if:

- **Adverse events probably/likely or certainly related to study drug, regardless of severity, occur in > 10% of enrolled patients, or**
- **Serious/life-threatening adverse events, regardless of causality, occur in > 2% of enrolled patients.**

11. Data Analysis:

Primary Endpoint

- 1) Compare opioid requirements (in morphine equivalents) between trauma patients with rib and/or sternal fractures receiving liposomal bupivacaine versus standard of care.

Secondary Endpoints

- 1) Compare clinical outcomes and treatment failures including:
 - a. Development of pneumonia, defined as >100,000 cfu/mL bacteria on bronchoalvelolar lavage, or clinically with leukocytosis, pulmonary infiltrate and fever
 - b. Median patient analgesic score by verbal NRS

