- c. Patients with known or suspected atrioventricular nodal blockade process requiring cardiology evaluation and/or pacemaker placement
- d. Hemodynamic instability (defined as a new intravenous vasopressor or inotrope requirement [e.g., norepinephrine; epinephrine; phenylephrine; dobutamine; milrinone] or a mean arterial pressure < 55 mmHg)
- e. Signs of active myocardial ischemia or non-ST elevation MI
- f. Patients with greater than 20 rib fractures (20-mL vial [266-mg dose]; 1-mL [13.3 mg] per rib)
- g. Weight < 50 kg or > 150 kg
- h. Pregnancy as defined by urine pregnancy test in all females of child-bearing potential
- i. Incarceration
- j. Inability to obtain informed consent
- k. Severe traumatic brain injury, GCS <8

Patients will be followed for outcome assessment during hospitalization through discharge.

14. Consenting process and plan

Patients will be identified as previously described and permission to consent per the trauma team attending will be obtained prior to administration of consent. Study personnel will administer consent in the patient's room. Patients who meet inclusion and exclusion criteria will be eligible for consent. Informed consent will be obtained prior to randomization into treatment arms. Patients unable to give consent will have LAR or next of kin consented. LAR must show proof of health care POA or court document. A copy of the documents will be kept with the

consent form. Next of kin is a person who may act as LAR without a document granted by court. Next of kin will be determined by team social workers' note. The order in which the next of kin may act as LAR is: spouse, parent, adult son or daughter, adult brother or sister. If next of kin available at the time of consent cannot agree, the person cannot participate in the research. Investigators will be available seven days a week and will continue correspondence with subjects throughout the study for up to 7 days or until hospital discharge, whichever comes first.

Subjects can withdraw from the study at any time per their desire or may be withdrawn at the discretion of the trauma team. Subjects will be withdrawn as appropriate based on any adverse event that may occur as described above in Section 9. Any subject who withdraws will be placed on standard of care.

15. Compensation:

Patients will not receive any compensation for research involvement.

16. Subject costs:

There are no additional costs to subjects.

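### Pneumonia and adverse events are looked for only until discharge, so observation time depends on length of stay, which the treatment aims to shorten

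*Combined protocol and SAP*

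**What the plan says.** Section 6 (Intervention) describes daily follow-up by coordinators and physicians for 96 hours after the block, "then daily by the trauma service physicians for 14 days or until discharge from the hospital if it occurs earlier". It ties safety recording to that period: "During this time all adverse events will be recorded". For patients with a serious adverse event, it adds: "If necessary these patients will be followed up by weekly phone calls as well as at the standard of care clinic visit".

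Section 5 (Study design) says: "Patients included in the study will be followed during inpatient hospitalization through discharge". Section 13 repeats this for outcomes: "Patients will be followed for outcome assessment during hospitalization through discharge".

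Section 11 lists as secondary endpoint 1a: "Development of pneumonia, defined as >100,000 cfu/mL bacteria on bronchoalvelolar lavage, or clinically with leukocytosis, pulmonary infiltrate and fever". It gives a diagnostic definition but no time window. Nominal outcomes are compared by Fisher's exact or chi-square test. ICU and hospital length of stay are secondary endpoints too, and the Study Justification gives the treatment's purpose as "minimizing adverse outcomes and length of stay and overall narcotic usage".

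**The concern.** The period over which a patient can be counted as having pneumonia or an adverse event is fixed by that patient's discharge date. Discharge happens after randomisation and is something the treatment is meant to bring forward. If it does so, patients in the active arm are watched for less time. A pneumonia that develops at home is missed more often in that arm, and the crude proportion looks better without a true difference. The comparison is therefore hardest to interpret in the situation the trial hopes to produce.

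The safety side does not need a difference between arms. A patient who goes home well and is readmitted has, by the Section 9 definition, a serious adverse event. No step is set up to find it unless that patient had an earlier serious event, yet the Section 10 stopping rule depends on the count of such events.

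**Working it through.** The plan states no figure on this point that could be reproduced, so the check is mainly a reading of the text.

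**1. Where collection ends**

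| Place | Activity | End |
|---|---|---|
| Section 6, Intervention | Daily follow-up and adverse event recording | Day 14, or discharge if earlier |
| Section 5, Study design | Follow-up | Discharge |
| Section 13 | Outcome assessment | Discharge |
| Section 6, after a serious event | Calls and two-week clinic visit, if needed | Resolution of the known event |
| Section 9, Safety Assessments | Every adverse event is entered in the database | No end given and no method of finding events |

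For a patient discharged before day 14, the first three rows all end at discharge. The fourth row tracks an event already known. The fifth governs recording once someone reports an event; it does not make anyone look.

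**2. Does the analysis compensate?** No. Section 11 specifies tests on proportions, with no person-time, censoring or competing-risk method for pneumonia.

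**3. How the mechanism works, with assumed inputs.** The documents give neither stay nor pneumonia risk. Suppose the true daily hazard h is the same in both arms and events are seen only until the earlier of discharge (day L) and day 14:

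- observed risk = 1 − exp(−h × min(L, 14))
- for a 14-day risk of 10%, h = −ln(0.90)/14 = 0.00753 per day
- stay of 8 days: 1 − exp(−0.0602) = 0.0584
- stay of 7 days: 1 − exp(−0.0527) = 0.0513
- apparent risk ratio = 0.0513/0.0584 = 0.88, although the true ratio is 1

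In the front-loaded version (3-day half-life, λ = ln 2/3), the share of 14-day events seen by day t is (1 − exp(−λt))/(1 − exp(−14λ)). That gives 0.877 at day 8 and 0.834 at day 7, a ratio of 0.95.

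| Assumed stay, control vs active (days) | Constant hazard, fixed stay | Constant hazard, stay varies between patients | Front-loaded hazard, fixed stay |
|---|---|---|---|
| 8 vs 7 | 0.88 | 0.91 | 0.95 |
| 8 vs 6 | 0.75–0.76 | 0.80–0.81 | 0.89 |
| 10 vs 7 | 0.70–0.72 | 0.79–0.80 | 0.89 |

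Ranges cover 14-day risks of 5% to 20%. The middle column uses a 3-day minimum plus an exponential excess, with observation capped at day 14. With a common 14-day window every entry is 1.00 by construction. With equal stay in the two arms, the ratio is also 1.00. The table shows direction only; it does not predict this trial.

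**4. Stopping rule.** Section 10 stops the study when serious or life-threatening events, whatever their cause, exceed 2% of enrolled patients. At full enrolment, 2% × 200 = 4, so a fifth affected patient crosses the line. At that threshold, a few missed readmissions could matter.

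**5. Can one contact close the window?** Counting days from injection, a patient discharged on day d has the two-week clinic visit on day d + 14. Since d ≥ 0, the visit never falls before day 14, so one contact covers the whole window.

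**The case against.** **The bias is conditional and unproven.** It needs stay to differ between arms. These are multi-system trauma patients, whose other injuries may well drive discharge. Patients who develop pneumonia are likely to be kept in, and those sent home are presumably well, so the hazard after discharge may be low. The illustration carries the in-hospital hazard past discharge and so leans towards overstatement. All of this stands, and it limits the point to a possible bias of unknown size.

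**In-hospital pneumonia is a coherent endpoint.** The definition needs a lavage culture or hospital findings, which a phone call cannot supply. This stands in part. It is why reported cases need confirmation from records and why in-hospital pneumonia should stay as a sensitivity analysis. It does not make the window equal between arms.

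**The discharge clause may qualify only the second phase of follow-up.** On that reading the first 96 hours carry no discharge cut-off. Even so, no method of contact after discharge is described, and the remaining days still end at discharge.

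**The follow-up statements do not truly conflict.** A reader might infer a contradiction between the 14-day limit, follow-up through discharge, and the Section 14 line that investigators "will continue correspondence with subjects throughout the study for up to 7 days or until hospital discharge, whichever comes first". The documents do not support that. The first is daily clinical follow-up, the second must run to discharge because hospital stay is an endpoint, and the third is about correspondence. They can coexist.

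**Conclusion.** The point holds as a conditional weakness in one secondary comparison and in safety ascertainment. For patients without an earlier serious event, nothing looks for pneumonia or adverse events after discharge, and the analysis of proportions does not allow for unequal observation. If the active arm goes home sooner, the pneumonia comparison could favour it. Whether or not stay differs, serious events after discharge could be missed from the stopping count. The size cannot be computed from the documents and may be small.

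Three stronger readings are not supported:

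- **That a planned test of adverse events between arms is biased.** Section 11 lists no such test, and the Section 10 thresholds apply to enrolled patients as a whole.
- **That the primary result is compromised.** The opioid comparison does not depend on finding pneumonia or adverse events after discharge.
- **That part of the drug's 96 hours of action goes unmonitored.** Telemetry is worded as 96 hours for all injected patients (Section 6, Intervention), 96 hours or discharge if earlier (Section 6, Schedule), and at least 96 hours (Section 9). A shortfall follows only if the second wording governs and a patient leaves early. Harmonising the three is an editorial matter and no evidence for this point.

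This is a cheap improvement worth making. It changes what the pneumonia comparison can support.

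**What to change.** Add one window to Section 6 (follow-up) and to Section 11, endpoint 1a. Suggested text:

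> Pneumonia, adverse events and serious adverse events are collected if their onset falls between injection (randomisation, for a patient not injected) and day 14, in all randomised patients, discharged or not. For patients discharged before day 14, blinded study staff complete collection by a chart check plus either one phone call on or after day 14 or the clinic visit two weeks after discharge, asking about new events and readmissions. Any reported pneumonia is confirmed against the Section 11 definition from the treating hospital's records. Patients not reached are reported by arm. Pneumonia with onset before discharge is a sensitivity analysis.

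Events with onset after day 14 in patients still in hospital should go on being recorded and be reported separately. Follow-up of known serious events to resolution stays as it is.

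Leave follow-up through discharge in Sections 5 and 13. ICU and hospital stay, adjunct use and cost need it, and a blanket day-14 limit would truncate them. Add there only the day-14 window for pneumonia and adverse events. Section 14 needs a clause allowing the extra contact.

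The cost is a few wording changes, a records-release line in the consent form if it has none, and a chart check with one short contact for at most 200 patients by existing staff. Events will still be found less completely after discharge than in hospital, and that shortfall falls on patients who leave early. The bias is therefore reduced, not removed, which is why the number not reached should be shown by arm.
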